5.6. Early Study Termination

Sponsor may discontinue the study at any stage for any reason or no reason. Possible reasons for early termination may include unanticipated adverse device effects that may present unreasonable patient risk.

The Study Steering Committee assists Sponsor in making a final decision for early study termination based on Data Safety Monitoring Board (DSMB) recommendations (refer to Section 14).

If the study is terminated early, the sponsor will provide a written statement describing why premature termination has occurred, and notify the Investigator, Institutional Review Board (IRB) and the regulatory authority (if applicable). All applicable clinical study documents will be subject to the same retention policy as detailed in Section 17.

5.7. Measures Taken to Avoid/Minimize Bias

This is a randomized, double-blinded, and sham-controlled study. The study design minimizes the bias of placebo effect, patient selection, and the effect of lifestyle intervention. The outcome data will be collected by the Investigator or study coordinator who are masked to the intervention, thus minimizing Investigator bias.

Subjects in both groups and at all study sites will be provided with the same lifestyle educational materials. Site personnel will be trained in the delivery of the centrally prescribed lifestyle modification intervention prior to the onset of the study and will receive ongoing supervision during the study to ensure treatment fidelity across study sites.

An independent Clinical Events Committee (CEC) will be established to adjudicate safety events as described in Section 13. The CEC will be masked to the subject's intervention, thus minimizing bias in safety assessment. A Data Safety Monitoring Board (DSMB) (Section 14) will be established to monitor and evaluate the safety data throughout the study.

6. STUDY ENDPOINTS

6.1. Primary Effectiveness Endpoints

The effectiveness of the TPS will be assessed by the following co-primary endpoints:

- Mean percent total body weight loss (% TBL) between the Treatment and the Control group at 12 months after the index procedure.
- The proportion of subjects in the Treatment group who achieve $\geq 5\%$ TBL at 12 months after the index procedure.

6.2. Secondary Effectiveness Endpoints

The following secondary endpoints will be assessed in this study:

- Proportion of subjects who achieve at least 7% and 10% TBL at 12 months in the Treatment versus Control group
- Percent total body weight loss over 12 months in the Treatment versus Control group
- Percent excess weight loss over 12 months in the Treatment versus Control group
- Proportion of subjects who achieve at least one obesity class reduction at 12 months in the Treatment versus Control group
- Change of BMI over 12 months from baseline in the Treatment group
- Change in weight-related quality of life over 12 months as assessed by IWQOL-Lite Questionnaire
- Change in eating behavior over 12 months as assessed by the Eating Inventory
- Change in appetite, hunger and fullness over 12 months as assessed by Visual Analog Scales.
- Change in comorbid conditions over 12 months in the Treatment group:
 - a) Prevalence of the metabolic syndrome and its individual components
 - b) Glucose, insulin, and insulin resistance (as estimated by HOMA)
 - c) High sensitivity C-reactive protein (hsCRP)
 - d) Lipid levels (LDL-C, HDL-C, and triglycerides)
 - e) Blood pressure
 - f) Waist circumference

6.3. Safety Evaluations

The overall device safety profile is characterized by assessing the incidence of adverse events (AEs), serious adverse events (SAEs), serious adverse device effects (SADEs), and unanticipated serious adverse device effects (UADEs) as detailed in Section 12. No formal hypothesis testing will be performed.

7. PATIENT SELECTION AND WITHDRAWAL

7.1. Study Population

Subjects with a BMI of 30.0-40.0 kg/m² who meet the inclusion and exclusion criteria will be evaluated for participation in the study. To ensure the safety of the subjects during weight loss, we aim to enroll individuals with controlled weight-related co-morbidities, such as Type 2 diabetes, hypertension, and hyperlipidemia. Conversely, individuals with a recent cardiovascular event and those with serious internal organ disease will be excluded.

The pivotal study cohort will consist of 270 subjects that will be enrolled from up to twelve study sites in the US, with no one site enrolling more than 25% of the total number of subjects in the pivotal cohort.

7.2. Inclusion Criteria

1. Male and female subjects between the ages of 22 to 60
2. A BMI between 30.0 to 40.0 kg/m², inclusive. Subjects with a BMI of 30.0 kg/m² to 34.9 kg/m² are required to have one or more of the following obesity-related mild-moderate comorbidities:
 - a. Type 2 Diabetes: meet one of the following criteria and currently not using insulin
 - i. HbA1c 6.5%-7.5%
 - ii. Controlled, on stable dose of oral medications for at least 3 months
 - b. Hypertension: meet one of the following criteria:
 1. Arterial blood pressure >140 mmHg systolic or >90 mmHg diastolic on or off hypertensive medication
 2. Arterial blood pressure ≤140 mmHg systolic and ≤90 mmHg diastolic on hypertensive medication
 - c. Hyperlipidemia, meeting at least one of the following criteria:
 - i. Fasting blood total cholesterol level of ≥240 mg/dl
 - ii. Fasting total triglyceride level of ≥200 mg/dl
 - iii. Low density Lipoprotein cholesterol ≥160mg/dl
 - iv. Currently taking lipid-lowering medication based on an elevation of total cholesterol, triglycerides, or LDL
3. History of obesity for at least 2 years, with history of failure of medically or commercially supervised weight loss program
4. History of weight stability (defined as a < 5% change in body weight) for at least 3 months prior to the screening visit
5. Female subjects of childbearing potential must have a negative urine pregnancy test and must commit to practice their physician-agreed form of birth control for the duration of participation
6. Willing and able to provide written informed consent
7. Willing and able to comply with study procedures and return for all study visits

7.3. Exclusion Criteria

1. Pregnancy or planned pregnancy in next 12 months after enrollment
2. Nursing or pregnancy within the 6 months prior to enrollment
3. Known hormonal or genetic cause for obesity
4. Prior history of any surgery or endoscopic intervention that has altered the esophageal, gastric, or duodenal anatomy, including any bariatric surgery, such as gastric bypass, and restrictive procedures such as laparoscopic adjustable gastric banding
5. Prior treatment with an intragastric balloon for the purpose of weight loss, where the balloon was removed less than 12 month prior to the screening visit for this study
6. Chronic use (in the past 6 months) of medications likely to contribute to weight gain or prevent weight loss (e.g., corticosteroids, lithium, olanzapine, risperidone, clozapine, anticonvulsants, glitazones (e.g., pioglitazone), monoamine oxidase inhibitors)
7. A history of gastric or duodenal ulcers
8. After treatment for *Helicobacter pylori*, subject still tests positive for *H. pylori*
9. A history of severe dyspepsia
10. GI tract motility disorders such as esophageal motility disorders, gastroparesis diabeticorum, or intractable constipation
11. History of inflammatory disease in the GI tract, such as Crohn's disease
12. History of coeliac disease
13. History of pancreatitis
14. History of portal hypertension, cirrhosis, and/or varices

15. Diabetes treated with insulin or significant likelihood of requiring insulin treatment in the next 12 months
16. HbA1c >7.5%
17. Uncontrolled thyroid and adrenal gland disease
18. Uncontrolled hypertension defined as systolic blood pressure > 160 mmHg or diastolic blood pressure > 100 mmHg
19. A history of cardiac arrhythmia, ischemic heart disease, myocardial infarction or chronic heart failure
20. History of cerebrovascular disease, transient ischemic attack or stroke
21. Presence of localized or systemic infection
22. Anemia (hemoglobin < 11.0 g/dl for female and < 12.0 g/dl for male)
23. History of asthma likely to require systemic steroid therapy during the duration of the study participation or frequent use of rescue inhalers
24. Autoimmune connective tissue disorders or known to be immunocompromised or at risk of becoming immunocompromised (e.g., HIV positive)
25. A history of malignancy except non-melanoma skin cancer
26. Continuous therapy with known ulcerogenic medication (e.g., aspirin greater than 81mg/day, NSAIDs)
27. On anticoagulant therapy (e.g., Coumadin, Warfarin, Heparin Pradaxa, Xarelto, Plavix)
28. Unwilling to avoid use of any weight-loss medication, including over-the-counter treatments and/or herbal supplements during the course of study, or on prescription medications that can be used for weight loss, even if they are not prescribed for weight loss (e.g., Topiramate, Wellbutrin) and stimulant medications (e.g., for ADHD)
29. Currently participating or unwilling to avoid participation in any non-study-related organized weight-loss program (medical or commercial) during the course of the study
30. Unable to take proton pump inhibitors (a daily 40+ mg of Omeprazole or equivalent), or addition of PPI may cause adverse drug interaction with subject's medication or interruption of treatment
31. Clinically significant abnormal laboratory values or an EKG that make the subject a poor study candidate in the opinion of the Investigator
32. Inability to walk at least 0.8 kilometers per day (10 minutes of continuous walking)
33. Planned surgical procedure that can impact the conduct of the study
34. Started on a prescribed concomitant medication regimen within the last three weeks, or whose concomitant medication regimen is expected to change during the course of the study, and where the Investigator determines the medication may affect the study outcome
35. Known allergy to any component materials in the TPSS including silicone, barium sulfate, and parylene
36. Current smoker or user of nicotine product or smoking cessation within 1 year of the screening date
37. Current abuse of drug or alcohol or past treatment for substance abuse
38. Presence of any severe uncontrolled psychiatric illness
39. Inpatient psychiatric treatment within the past year
40. A score of ≥ 10 on the Patient Health Questionnaire 9 (PHQ-9), indicating moderate depression
41. Diagnosis of bulimia nervosa or binge eating disorder
42. Any medical condition (including psychiatric disease) that would interfere with the interpretation of the study results, the conduct of the study, or would not be in the best interest of the subject in the opinion of the site Primary Investigator
43. Participation in another clinical study within 60 days of screening date, in a previous or ongoing clinical study, or plan to participate in another clinical study at any time during this study
44. Employee or family member of BAROnova, the Investigator, or site study staff
45. The Investigator judges the candidate unsuitable for the study

46. Have any of the following endoscopic exclusion criteria:

- a. Esophageal stricture
- b. Barrett's esophagus
- c. Erosive esophagitis
- d. Varices
- e. Angiectasias
- f. Gastric mass
- g. Antral or peri-pyloric polyps
- h. Peptic ulceration
- i. Hiatal hernia ≥ 4 cm
- j. Pyloric stricture
- k. Any other abnormalities or characteristics that preclude safe use of the TPS

7.4. Point of Enrollment

The point of enrollment occurs when a subject or subject's legally authorized representative has provided written informed consent and the TPSS Access Sheath has been introduced in the subject during the index procedure.

7.5. Patient Discontinuation

Once enrolled, each subject will remain in the study until the required follow-up period is complete. However, the subject has the right to withdraw from the study at any time without penalty or loss of benefit. The following events will result in terminating the subject's follow-up:

- Subject voluntary withdrawal
- Subject withdrawn by the Investigator as clinically indicated
- Subject becomes pregnant
- Subject lost to follow-up
- Subject death
- Study is terminated according to Section 5.6 (Early Study Termination)

In the case of subject withdrawal from the study, the TPS must be removed before the subject exits the study.

In case the TPS is removed early as described in Section 10.5, the subject's participation in the study is considered terminated. Any Adverse Events will be followed until resolution or stabilization according to Section 12.1.

In case a subject achieves normal BMI (≤ 22 kg/m²) for two consecutive visits before the 12-month follow up, the subject is considered to have completed the study. Subject will exit the study and the device should be removed in the treatment subjects.

A final endoscopy should be performed whenever possible before the Treatment subject exits the study.

The Sponsor must be notified of the reason for subject discontinuation. The site will document this information on the electronic case report form (eCRF) and make every effort to give a full description of the reason for withdrawal. Investigators must also report this information to the local IRB as defined by their institution's procedure.

Subjects who are terminated early will not be replaced by enrolling additional subjects.

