12.1. Adverse Events

An AE is any untoward medical occurrence in a subject or clinical investigation subject that occurs during any part of the clinical study, whether related to the investigational device or not. Pre-existing conditions are not reported as AEs unless there has been a worsening in severity or frequency which cannot be attributed to the disease's natural history or progression. Protocol-defined follow-up visits and pre-scheduled endoscopies (including device placement/removal, patient surveillance, and planned diagnostic endoscopies) are not considered adverse events.

For AEs, the event description, severity, date of onset, treatment, outcome, and relationship to device will be collected on the AE eCRF.

All procedure- and device-related AEs must be followed until resolution or stabilization (the Investigator does not expect any further improvement or worsening of the event).

An Adverse Device Effect (ADE) is any adverse event that is considered possibly-related or related to the device. An ADE may occur at any time after exposure to the investigational device.

Determination of whether there is a reasonable possibility that the investigational device caused or contributed to an AE will be reported by the Investigator and reviewed by the CEC as described in Section 12.2.

Determination will be based on assessment of temporal relationships, biologic plausibility, association (or lack of association) with underlying disease, and presence (or absence) of more-likely cause.

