12.1.3. Unanticipated Adverse Device Effects

Unanticipated adverse device effects (UADE) are any serious adverse device effects on health or safety or any life-threatening problem or death caused by, or associated with, the investigational study device if that effect, problem, or death was not previously identified in nature, severity or degree of incidence in the investigational plan or application (including IFU) or any other unanticipated serious problem associated with a device that relates to the rights, safety, or welfare of subjects.

When an AE meets the definition of a UADE or that relationship is unknown, the Investigator will report the event to BAROnova within 24 hours but no later than 10 working days after the Investigator first learns of the effect and reports to the reviewing IRB as required.

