12.3.2. Clinical Site Reporting Requirements

- All AEs and ADEs will be recorded by the Investigator or designee on the eCRFs provided
- Any SAEs are to be reported to the Sponsor within 36 hours except UADE or suspected UADE which is to be reported within 24 hours of knowledge of the event, followed by a written confirmation by the Investigator within 5 working days
- The Investigator at each site is ultimately responsible for reporting AEs, SAEs and UADEs to the IRB according to local IRB requirements

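### Section 7.5 ends follow-up at pregnancy, and no available text requires the site to seek the outcome of a pregnancy with no open adverse event at exit, although fetal and congenital outcomes count as SAEs

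*Combined protocol and SAP*

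**What the plan says.** Section 7.5 introduces its list with "The following events will result in terminating" the subject's follow-up, and "Subject becomes pregnant" is one of the items, with no exception attached. Section 10.5 also names pregnancy as a reason to consider early device removal. Under 7.5 early removal ends participation, and under 10.5 control subjects are handled as if they had the device.

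For a subject whose device is removed early, 7.5 adds: "Any Adverse Events will be followed until resolution or stabilization according to Section 12.1". Section 12.1 states the duty as "All procedure- and device-related AEs must be followed until resolution or stabilization". It defines an AE as something that "occurs during any part of the clinical study", and it also says "An ADE may occur at any time after exposure to the investigational device".

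Reporting starts from what the site knows. In 12.1.3 the outer time limit for a UADE runs from a point "after the Investigator first learns of the effect". In 12.3.2 a UADE or suspected UADE is due "within 24 hours of knowledge of the event".

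Section 12.1.1 and Appendix A (item 54) both include fetal and congenital outcomes in the SAE definition. Appendix B schedules urine pregnancy tests at screening and baseline only.

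**The concern.** The plan creates a class of serious adverse event that usually becomes observable only as a pregnancy advances or ends. It also stops follow-up when the pregnancy is the reason for exit. Anyone reading the final safety table would assume that the absence of such events means they were looked for.

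Each device-exposed pregnancy would be informative as an individual case. Section 3.5.4 says clinical experience with the device is limited, and the anticipated events in 3.5.2 include malnutrition and changed absorption of medicines. Pregnancy is also foreseeable: women from age 22 are eligible, 18 of 20 subjects in the feasibility study were female (Section 3.4.3), and both 7.5 and 10.5 plan for it. What is at stake is how a few cases are ascertained and how honestly a zero can be read. Outcomes in control subjects would say little about the device.

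**Working it through.** No arithmetic applies. The check takes a subject who becomes pregnant, feels well and has no adverse event, and asks at each step whether any available provision leads the site to learn how the pregnancy ended.

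1. **Exit.** Under 7.5 her follow-up ends. If she has the device, removal under 10.5 also ends participation. A control subject exits in the same way.
2. **Follow-up of adverse events after exit (7.5).** This sentence follows events that exist. Neither 12.1 nor Appendix A defines pregnancy itself as an AE, so an uncomplicated pregnancy leaves nothing open to follow. Had a complication been open at exit, it would be covered.
3. **The 12.1 duty.** It covers procedure- and device-related AEs until they resolve or stabilise. Again it needs an event to start from.
4. **Late device effects (12.1).** The statement that an ADE can arise at any time after exposure allows a late outcome to count. It does not tell anyone to look for one.
5. **Reporting rules (12.1.3 and 12.3.2).** The time limits start when the site becomes aware. An outcome that the subject volunteers could be reported; one that she does not mention would not be.
6. **Removal visit (11.9.10.1).** After study exit, follow-up reverts to usual clinical care. No study contact is added.
7. **Lost-to-follow-up procedure (7.6).** The calls and certified letter are for subjects who stop attending without withdrawing, not for those whose follow-up 7.5 has ended.
8. **Schedule (Appendix B).** No contact about a pregnancy outcome appears.

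For this subject, no step requires the outcome to be sought. For a subject with an open AE at exit, steps 2 and 3 give cover for that event. The gap is therefore limited to pregnancies with no open AE at exit.

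On the reporting side, 7.5 requires the reason for discontinuation to be recorded and 15.5.1 tabulates reasons for withdrawal, so the number of pregnancy exits will be visible. Section 15.5.5 summarises AEs, SAEs and UADEs by count and percentage. It does not ask how many pregnancy outcomes were obtained, so a zero for fetal and congenital SAEs could not be told apart from missing information.

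**The case against.** The strongest reply is that this is an argument from silence in a partial record. The consent pages, Sections 5.4, 5.5, 15.5.6 and 15.5.7, the CEC charter, the IFU and the eCRF were not available, and contact after exit with the subject's agreement is a natural item for a consent form. This stands as a limit: a provision there cannot be excluded. Against it, 7.5 and 12.1 are the natural homes for such a rule and are available, and Section 14 ties 5.4 and 15.5.6 to staged safety monitoring.

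A second reply is that 7.5 speaks of following any adverse event, so a complication present at exit would not be dropped. That is a fair reading and is accepted here. A reader might infer that all safety observation stops at pregnancy; the documents do not support that.

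A third reply is that reporting duties always depend on what the site knows. True, and the reporting rules are not at fault. The missing element is a step that brings the outcome to the site's knowledge.

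A fourth reply is that few cases will arise. Planned pregnancy is excluded (7.3 item 1), birth control is required (7.2 item 5), safety is descriptive with no hypothesis test (6.3), and pregnancy exits will be visible in the withdrawal table. All of this stands and keeps the point minor.

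A reader might also want to say how many days each pregnancy goes unobserved. The documents do not support a figure. They give no time from conception to recognition, and 7.5 requires the device to be out before a withdrawn subject exits, so a treated subject may leave some time after the pregnancy is recognised.

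**Conclusion.** The point holds as a minor gap in safety ascertainment. As the available text reads, a pregnancy with no open adverse event at exit has an outcome that the plan classes as potentially serious but does not seek. The safety summary could then show no fetal or congenital SAE only because outcomes were not obtained.

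No number of cases and no length of unobserved time is claimed. If no subject becomes pregnant, nothing is lost. The co-primary endpoints, their analysis and the sample size do not depend on these outcomes. The conclusion assumes that no pregnancy provision sits in the parts that were not available. If one does, a cross-reference from 7.5 would settle most of the point. It would be wrong to infer that the trial has no pregnancy follow-up anywhere, or that its overall safety conclusions are unsound.

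**What to change.** - **Section 7.5:** state that pregnancy ends device treatment and weight assessments but not safety follow-up. With the subject's agreement, obtain the outcome by one telephone contact after the expected delivery date, or at the end of the pregnancy if that comes sooner, and record it on a short form. Do this in both arms, in keeping with the equal handling that 10.5 intends.
- **Section 12.1:** add that the outcome of a pregnancy that began during participation is reportable even if it becomes known after exit.
- **Section 15.5.5:** list any fetal or congenital SAE as an individual case, and give the number of pregnancies and the number of outcomes obtained. Make no comparison between arms. The mITT population stays as defined.

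The cost is a paragraph, a sentence, a short form and a few calls. Some outcomes will arrive after database lock and would be reported as an addendum.
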